### 3.2.2. Rationale for Dose Selection

The dose justification for pediatric patients aged  $\geq 6$  years to <12 years is based on the observed efficacy and safety in the dose ranging study in adult AD patients (R668-AD-1021), the observed efficacy and safety in the phase 3 monotherapy studies in adult AD patients (R668-AD-1334 and R668-AD-1416), the observed PK data, efficacy and safety results in a pediatric AD study of patients  $\geq 6$  to <18 years old (R668-AD-1412). The selection of these dosing regimens is further supported by population PK modeling.

The adult dose-ranging study evaluated dupilumab dose regimens of 300 mg QW, 300 mg Q2W, 300 mg once every 4 weeks (Q4W), 200 mg Q2W, and 100 mg Q4W versus placebo, administered for 16 weeks. All 5 dose regimens were efficacious. The mean pharmacodynamic

(PD) effect/efficacy of dupilumab (represented by change in EASI, IGA, and Pruritus Numerical Rating Scale [NRS] scores) at week 16 generally aligned in the same rank order as the total monthly dose and the mean concentrations of functional dupilumab at week 16. Thus, the 300 mg QW regimen was consistently the most efficacious dose regimen in this study across multiple endpoints, followed closely by the 300 mg Q2W dose regimen. Differences in the efficacy and safety outcomes between the 300 mg QW and 300 mg Q2W were relatively small. The 200 mg Q2W and 300 mg Q4W doses also showed good efficacy responses but were numerically inferior to the 300 mg Q2W and 300 mg QW regimens for the majority of efficacy endpoints. The efficacy of the 100 mg Q4W regimen (100 mg total monthly dose) appeared to be sub-optimal.

Study R668-AD-1412 was a phase 2a, multicenter, open-label, ascending-dose, sequential-cohort study investigating the safety, tolerability, PK, immunogenicity, and efficacy of single-dose and repeat-doses of dupilumab administered SC in pediatric patients with moderate to severe AD (for adolescents  $\geq 12$  to  $< 18$  years old) or severe AD (for school-going children  $\geq 6$  to  $< 12$  years old) that was not adequately controlled with topical treatments. The 2 assessed dose regimens at 2 mg/kg and 4 mg/kg correspond to the weight normalized dose in adults at 150 mg and 300 mg, respectively. Dupilumab administered as single and repeated weekly doses of 2 mg/kg and 4 mg/kg for 4 weeks was generally well tolerated with an acceptable safety profile in both pediatric age groups included in that study. There was a higher incidence of TEAEs following single and repeated weekly administration of 4 mg/kg compared to 2 mg/kg in both age-groups. This was driven by a higher incidence of nasopharyngitis and skin infections in the 4 mg/kg dose arm versus the 2 mg/kg dose arm. However, most of the adverse events (AEs) were mild in intensity, transient in nature, and not related to study drug. The most common AE reported after both single doses and repeated weekly doses was nasopharyngitis.

In children aged  $\geq 6$  to  $< 12$  years, dupilumab administered as a single dose of either 2 mg/kg or 4 mg/kg, in the study R668-AD-1412, induced a significant and rapid reduction of disease activity in patients at week 2 (37% and 33% reduction in EASI score from baseline for 2 mg/kg and 4 mg/kg doses, respectively). Repeated weekly doses of dupilumab led to a further improvement in disease severity in patients in both dose groups (76% and 63% reduction in EASI score from baseline for 2 mg/kg and 4 mg/kg doses, respectively, at week 12). There did not appear to be a clear dose response, as the 2 dose groups showed similar efficacy on the various endpoints evaluated during the study. The small sample size may have limited the precision of this study, but these data are consistent with saturation of the IL-4 receptor after 4 weekly doses of either 2 mg/kg or 4 mg/kg.

The collective clinical data on the exposure versus efficacy and safety in the adults and pediatric population as observed to date supports a similar exposure-response relationship for efficacy and safety between the adult and pediatric populations down to 6 years of age and justify the approach of selecting dose regimens for this study based on the criteria of matching adult exposure.

To account for body size difference in the pediatric population and taking into account the observed large therapeutic indices of dupilumab, a tiered fixed dosing regimen was chosen over weight based (mg/kg) dosing for ongoing development. This approach reduces the risk of dosing errors that can occur with weight-based dosing, as well as allowing for dosing convenience by simplifying administration using a prefilled syringe/device.

A population PK model was used to describe the exposure of dupilumab in the population identified in this protocol. This model, initially based on drug concentration data from studies conducted in adults, was further informed by the exposure data of the study(s) conducted in pediatric patients (R668-AD-1412). The PK modeling for dupilumab has shown weight to be the most important covariate influencing exposure, with exposure being inversely correlated with body weight. Outside of the effect of body weight on PK, the existing data do not suggest an age-related effect on exposure.

Data gathered from NHANES (n=1269) show that median weight in the children aged 6 to 11 years old is = 32 kg (Q1=25, Q3=42). Simulations from the PK model suggest that the adult dose regimens (300 mg QW and 300 mg Q2W) may lead to systemic exposure in these children that is greater than the maximum exposure observed in adults. Hence, these doses are not supported by the safety data obtained in adults and will not be studied in children.

For the 200 mg Q2W regimen in children aged  $\geq 6$  to  $< 12$  years old who weigh  $> 30$  kg, the simulated exposure substantially overlaps with the efficacious exposure in adults from studies R668-AD-1021, R668-AD-1334, R668-AD-1416 and R668-AD-1224 (300 mg Q2W and QW). In addition, in study DRI12544 (a phase 2b study in patients with moderate to severe uncontrolled asthma) (300 mg Q2W) a strongly positive benefit-risk was identified. Hence, the proposed 200 mg Q2W dosing regimen for children aged  $\geq 6$  to  $< 12$  years old weighing  $> 30$  kg is expected to have a significant clinical benefit with an appropriate safety profile, under the assumption that PK/PD relationship is similar in pediatrics and adult patients.

A dose regimen of 100 mg Q2W SC has not been evaluated to date in the dupilumab program. However, based on simulations from the PK model, the use of 100 mg Q2W is expected to provide mean exposure in children  $\geq 6$  to  $< 12$  years old who weigh  $< 30$  kg that is similar to that for 200 mg Q2W in children  $> 30$  kg, thereby supporting the use of this regimen in the lower weight group. Moreover, the 100 mg dose can be delivered using a lower volume of injection. Since volume of injection has been shown to be an important factor impacting the tolerability of SC injections (Heise 2014), the smaller injection volume associated with the 100 mg injection may offer some advantage in this population.

The 300 mg Q4W regimen was chosen to be included as a dosing option with less frequent injections. With this regimen, in children  $\geq 6$  to  $< 12$  years old and weight  $> 30$  kg, simulated dupilumab exposure at steady-state, specifically  $C_{max}$ ,  $C_{trough}$ , and weekly area under the curve (AUC) were lower than for the 200 mg Q2W. Study R668-AD-1021 demonstrated that efficacy for the 300 mg Q4W regimen was statistically superior to placebo in adults. Pharmacokinetic simulations have shown that in children with weight  $> 30$  kg, the steady-state exposure was higher for the 300 mg Q4W regimen than in adults with the same regimen, but is not expected to exceed that for adults receiving 300 mg Q2W.

In children with weight  $< 30$  kg, simulated mean weekly AUC at steady-state for the 300 mg Q4W regimen was similar to that in adults receiving 300 mg Q2W, while  $C_{max}$  was higher and  $C_{trough}$  was lower. Data gathered from this dose regimen will enable PK/PD modeling to better characterize the exposure-response relationship in pediatric patients. A less frequent dosing regimen is expected to enhance compliance, especially in a pediatric population.

The administration of the loading dose of dupilumab will allow systemic concentrations to reach effective concentrations faster, and potentially reduce the time to onset of clinical effect.

### 3.2.3. Safety Considerations

R668-AD-1412 was a phase 2 study to evaluate the PK and safety of dupilumab in patients aged  $\geq 6$  years to  $< 18$  years, with moderate-to-severe AD. Dupilumab administered as single and repeated weekly doses of 2 mg/kg and 4 mg/kg for 4 weeks was generally well tolerated with an acceptable safety profile in both pediatric age groups (12 to 17 years old and 6 to 11 years old) included in this study. There was a higher incidence of TEAEs after administration of a single dose of 4 mg/kg as compared to 2mg/kg dose in both age-groups. Similarly, there was a higher incidence of TEAEs after administration of repeated weekly doses of 4 mg/kg as compared to repeated weekly doses of 2 mg/kg in both age-groups. This was driven by a higher incidence of nasopharyngitis and skin infections in the 4 mg/kg as compared to 2 mg/kg dose arm. The most common AE reported after both single doses and repeated weekly doses was nasopharyngitis.

In children 12 to  $< 18$  years old, there were 2 SAEs reported in each dose group (in the 2 mg/kg group, the SAEs reported were palpitations and infected AD; in the 4 mg/kg group, the SAEs reported were staphylococcal skin infection and infected AD). In children 6 to 11 years old, 2 patients in the 4 mg/kg dose group had serious TEAEs (2 events of exacerbation of AD, septic arthritis of the hip joint, and infected AD). None of these serious TEAEs was assessed by the investigators as drug-related. The events of infected AD and staphylococcal skin infections occurred in patients who were not being treated with dupilumab at time of onset of the SAE (patients were either in follow-up period of part A or in follow-up period of part B). It is well known that a very high proportion of patients with AD have skin colonization ([Ong 2010](#)) and patients with AD are prone to developing skin infections. Dupilumab, by treating AD, should lead to a reduction in skin infections. This is supported by data from phase 3 trials in adults with AD in which the incidence of serious and severe infections was numerically higher in the placebo group as compared to dupilumab (0.5% to 1% dupilumab and 2% to 3% placebo).

Positive anti-drug antibody (ADA) was observed in 50 patients (64.9 %) at any time, 31 of which (40.3% out of total) were categorized as persistent treatment-emergent ADA. The rate of occurrence of persistent ADA were similar across cohorts with a trend of higher rates in the adolescents compared with school-going children. Six patients (12.0%) had high titers ( $> 10,000$ ), 4 from the 2 mg/kg groups and 2 from 4 mg/kg groups. Within each age group, there also seemed to be a trend for higher incidence of persistent ADA in lower dose cohorts as compared to higher dose cohorts. Dupilumab concentrations in patients with high titers were markedly reduced compared to those with a negative response, or low or moderate titers. These patients had an inferior clinical response to the study drug as compared to the overall study population. The high titer ADAs were not associated with any systemic symptoms of hypersensitivity in these patients, although one of these patients did experience an injection site reaction, which was mild in intensity.

Standard safety monitoring used in previous trials with dupilumab is planned to be conducted during this study. An internal safety monitoring team will be reviewing blinded data at regular intervals during the study to monitor the safety of patients. An Independent Data Monitoring Committee (IDMC) overseeing the entire dupilumab clinical development will be in place for the duration of the study to monitor the safety of the patients and to provide the sponsor with appropriate recommendations in due time to ensure the safety of the patients.

Additional information can be found in the Investigator's Brochure.

### 3.2.4. Risk/Benefits of Participating in the Study

#### 3.2.4.1. Benefits

The efficacy and safety of dupilumab in adults was evaluated in 4 randomized, double-blind, placebo-controlled studies and 1 dose-ranging study in patients with moderate-to-severe atopic dermatitis. In all studies, dupilumab treatment consistently reduced both the extent and severity of lesions as well as the severity of pruritus.

The first clinical study of dupilumab in pediatric patients aged 6 years to <18 years old has been completed (R668-AD-1412). Dupilumab administered as single and repeated weekly doses provided significant clinical benefit to pediatric patients in both age groups (6 years to 11 years and 12 to <18 years) consistent with that observed in adults.

#### 3.2.4.2. Risks

Of the adverse drug reactions identified in the dupilumab adult AD clinical program, injection site reactions were very common ( $\geq 10\%$ ). Common adverse reactions ( $\geq 1\%$  and  $< 10\%$ ) included conjunctivitis, allergic conjunctivitis, eye pruritus, blepharitis, oral herpes, eosinophilia, and headache.

Serum sickness and serum sickness-like reactions occurred very rarely ( $< 0.01\%$ ) (Dupixent [SmPC], 2017).

In the pediatric trial, the safety profile was consistent with that reported in adults. There were no new safety signals detected with dupilumab in the pediatric population.

One serious case each of serum sickness and serum sickness-like reaction (both associated with high ADA titers) were reported in adult AD studies. Additionally, there has been 1 report of anaphylaxis considered related to study drug by the investigator in an asthma study (Dupilumab [Investigator Brochure, 2017]). No AEs of systemic hypersensitivity were reported in the pediatric study. In study R668-AD-1652, patients will be monitored at the trial site for 2 hours post-dose for the first 3 visits at which study drug is administered to facilitate detection and treatment of any immediate hypersensitivity reactions to the study drug.

A higher incidence of conjunctivitis-related events has been observed in dupilumab-treated subjects as compared to placebo in the AD studies. A predominant number of these cases were non-serious, mild to moderate in severity, reported recovered/recovering during the active study periods, and infrequently led to study drug discontinuation. Neither a consistent dose response nor a consistent time to onset of these events have been observed.

Similarly, a higher incidence of injection site reactions has been observed in the dupilumab treated subjects, consistent with the subcutaneous injection of a protein biologic. There have been no serious events of ISR, and these events have infrequently led to study drug discontinuation (Dupilumab [Investigator Brochure, 2017]).

#### 3.2.4.3. Risk/Benefit Conclusion

The safety data available to date, in conjunction with the risk monitoring and mitigation strategies in the study protocol, and the clinical benefit of dupilumab demonstrated in multiple AD studies, support a favorable benefit-risk profile for dupilumab.

## 4. STUDY VARIABLES

### 4.1. Demographic and Baseline Characteristics

Baseline characteristics will include standard demography (eg, age, race, weight, height, etc.), disease characteristics including medical history (including asthma), and medication history for each patient.

### 4.2. Primary and Secondary Endpoints

#### 4.2.1. Primary Endpoint

The primary endpoint in the study is:

- Proportion of patients with IGA 0 or 1 (on a 5-point scale) at week 16

For the EMA and EMA Reference Market Countries only, the co-primary endpoints are:

- Proportion of patients with EASI-75 ( $\geq 75\%$  improvement from baseline) at week 16
- Proportion of patients with IGA 0 or 1 (on a 5-point scale) at week 16

#### 4.2.2. Secondary Endpoints

The key secondary endpoints are:

- Proportion of patients with EASI-75 ( $\geq 75\%$  improvement from baseline) at week 16 (this is not a secondary endpoint for ex-US countries as it is already a co-primary endpoint)
- Percent change in EASI score from baseline to week 16
- Percent change from baseline to week 16 in weekly average of daily worst itch score

Other secondary endpoints are:

- Change from baseline to week 16 in weekly average of daily worst itch score
- Proportion of patients with EASI-50 at week 16
- Proportion of patients with EASI-90 at week 16
- Change from baseline to week 16 in percent Body Surface Area (BSA) affected by AD
- Percent change from baseline to week 16 in Scoring Atopic Dermatitis (SCORAD)
- Proportion of patients with improvement (reduction) of weekly average of daily worst itch score  $\geq 4$  from baseline at week 16
- Proportion of patients with improvement (reduction) of weekly average of daily worst itch score  $\geq 3$  from baseline at week 16
- Time to onset of effect on pruritus during the 16-week treatment period ( $\geq 4$  point reduction of weekly average of daily worst itch score from baseline)

- Time to onset of effect on pruritus during the 16-week treatment period ( $\geq 3$  point reduction of weekly average of daily worst itch score from baseline)
- Change from baseline to week 16 in Children's Dermatology Life Quality Index (CDLQI)
- Change from baseline to week 16 in Patient Oriented Eczema Measure (POEM)
- Change from baseline to week 16 in Dermatitis Family Index (DFI)
- Change from baseline to week 16 in Patient Reported Outcomes Measurements Information Systems (PROMIS) pediatric anxiety short form scale score
- Change from baseline to week 16 in PROMIS pediatric depressive symptoms short form scale score
- Topical treatment for AD – proportion of TCS medication-free days from baseline to week 16
- Mean weekly dose of TCS in grams for low- and medium-potency TCS from baseline to week 16
- Mean weekly dose of TCS in grams for high-potency TCS from baseline to week 16
- Incidence of skin-infection TEAEs (excluding herpetic infections) through week 16
- Incidence of serious TEAEs through week 16

#### 4.2.3. Other Endpoints and Assessments

Other endpoints and assessments, as applicable, will be specified in the statistical analysis plan (SAP).

#### 4.3. Pharmacokinetic Variables

Concentration of functional dupilumab in serum at each time point will be considered to be trough values ( $C_{\text{trough,timepoint}}$ ).

#### 4.4. Anti-Drug Antibody Variables

Anti-drug (dupilumab) antibody variables include status (positive or negative) and titer as follows:

- Total number of patients negative in ADA assay at all time
- Total number of patients positive in ADA assay at any time
- Total number of patients with preexisting immunoreactivity – defined as either an ADA positive response in the assay at baseline with all post-baseline ADA results negative, or a positive response at baseline with all post-baseline ADA titer  $< 4$ -fold over baseline titer level

- Total number of patients with treatment-emergent ADA response in ADA assay – defined as a positive response in the ADA assay post-first dose, when baseline results are negative, or missing. The treatment-emergent responses will be further characterized into the following categories:
  - Persistent ADA response – a treatment-emergent ADA positive response with 2 or more consecutive positives in the ADA assay separated by greater than a 12-week period, with no ADA negative samples in between
  - Transient ADA response – a treatment-emergent ADA positive response that is not considered persistent or indeterminate
  - Indeterminate ADA response – a treatment-emergent ADA positive response with only the last collected sample positive in the ADA assay
- Total number of patients with a treatment-boosted response – defined as a positive response in the ADA assay post first dose that is  $\geq 4$ -fold over baseline titer levels when baseline results are positive
- Titer value category
  - Low (titer  $< 1,000$ )
  - Moderate ( $1,000 \leq \text{titer} \leq 10,000$ )
  - High (titer  $> 10,000$ )

Anti-drug antibody positive samples will be further characterized for the presence of neutralizing antibody (NAb) response:

- Total number of patients positive in the NAb assay at the time points analyzed.

## 5. STUDY DESIGN

### 5.1. Study Description and Duration

This is a randomized, double-blind, placebo-controlled, parallel-group study in which study treatments (dupilumab/placebo) will be administered concomitantly with TCS. Approximately 330 study patients are planned to be enrolled in the study.

The study will consist of the following periods (Figure 2):

1. Screening of up to 9 weeks,
2. TCS standardization period of 2 weeks,
3. Treatment period of 16 weeks, and
4. Follow-up of 12 weeks (for patients who do not enter the OLE)

[figure not shown]
After the parents or legal guardians provide informed consent and patients provide assent, the patients will be assessed for study eligibility at the screening visit. During the screening period, systemic treatments for AD will be washed out, as applicable, according to the eligibility requirements (provided in Section 6.2.1 and Section 6.2.2). The use of TCS ( $\pm$ TCI) will be

permitted at the discretion of the investigator during the screening period until day -14. Starting on day -14, all patients will initiate a standardized TCS treatment regimen according to the guidelines in Section 7.2. Patients may be rescreened, unless the reason for the screen failure is related to failing the disease severity inclusion criteria. Patients should apply moisturizers twice daily for at least 7 days before randomization.

Patients who continue to meet eligibility criteria at baseline will undergo day 1/baseline assessments and will be randomized in a 1:1:1 ratio stratified by baseline body weight (<30 kg and  $\geq$ 30 kg) (Figure 1) and region (North America, Europe) as follows:

- dupilumab Q2W treatment group:
  - Patients with baseline weight <30 kg will receive Q2W SC injections of 100 mg dupilumab (0.7 mL of a 150 mg/mL solution) from week 2 to week 14, following a loading dose of 200 mg on day 1.
  - Patients with baseline weight  $\geq$ 30 kg will receive Q2W SC injections of 200 mg dupilumab (1.14 mL of a 175 mg/mL solution) from week 2 to week 14, following a loading dose of 400 mg on day 1
- dupilumab Q4W treatment group: all patients regardless of weight will receive Q4W SC injections of 300 mg dupilumab (2 mL of a 150 mg/mL solution) from week 4 to week 12, following a loading dose of 600 mg on day 1.
- placebo treatment group: Patients will receive matching placebo (including doubling the amount of placebo on day 1 to match the loading dose). In order to maintain blinding, the patients in the <30 kg weight stratum will be randomly assigned to receive, in a 1:1 ratio, either Q2W SC injections of placebo (0.7 mL) matching the 100 mg dupilumab (including doubling the amount of placebo on day 1 to match the loading dose) or Q4W SC injections of placebo (2 mL) matching the 300 mg dupilumab (including doubling the amount of placebo on day 1 to match the loading dose). In the  $\geq$ 30 kg weight stratum, the patients randomized to the placebo group will receive, in a 1:1 ratio, either Q2W SC injections of placebo (1.14 mL) matching the 200 mg dupilumab (including doubling the amount of placebo on day 1 to match the loading dose) or Q4W SC injections of placebo (2 mL) matching the 300 mg dupilumab (including doubling the amount of placebo on day 1 to match the loading dose).

Figure 1: Study Design

[figure not shown]

Arm A consists of patients receiving Q2W treatment, either 100 mg for patients weighing <30 kg or 200 mg for patients weighing  $\geq 30$  kg. Arm B consists of patients receiving Q4W treatment, 300 mg regardless of weight. Arm C consists of patients receiving placebo treatment Q2W and Q4W and matching the dupilumab Q2W and Q4W dose regimens.

During the treatment period, patients will have weekly in-clinic visits through week 4, and then in-clinic visits Q4W through week 16 with weekly telephone visits in between the in-clinic visits. Parents/caregivers will be trained on injecting study drug during in-clinic visit 3 (day 1), visit 5 (week 2), and visit 7 (week 4) (this only applies to patients who will receive Q2W treatment during the study). During weeks in which no in-clinic visit is scheduled, the parent/caregiver will administer study drug to the patient. In case the parent/caregiver does not want to administer study drug to patient, they may have the clinic staff administer all the study drug injections in the clinic. Safety, laboratory, and clinical assessments will be performed at specified clinic visits, as noted in [Table 1](#). The end of treatment period visit will occur at week 16, two weeks after the last dose of study drug for patients randomized to the Q2W treatment group or placebo Q2W group, and 4 weeks after the last dose of study drug for patients randomized to the Q4W treatment or placebo Q4W group. The co-primary endpoints will be assessed at this visit. If patients prematurely discontinue study treatment, the patients will be encouraged to stay in the study to have data collected at all remaining scheduled visits until completion of the planned end of study visit. Patients who participate in the study may subsequently be eligible to participate in an OLE study. All patients will be offered the opportunity to screen for entry into the OLE study at the end of the treatment period (week 16).

Patients who decline to enroll in the OLE study or those who fail eligibility criteria for the OLE study will have a 12-week follow-up period. For these patients, after week 16, follow-up visits will occur every 4 weeks from week 20 to week 28. During the follow-up period, patients will be monitored for safety and tolerability and have laboratory and clinical assessments as noted in [Table 2](#).

Figure 2: Study Flow Diagram

D = study day; W = study week

Note: The length of the screening period is not fixed, but the screening period and TCS standardization must not exceed 77 days. The length of the TCS standardization period is fixed at 14 days.

 For patients who enter the OLE, week 16 is the end of study.

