#### Analysis

All AEs reported in this study will be coded using the currently available version of the Medical Dictionary for Regulatory Activities (MedDRA®). Coding will be to lowest level terms. The verbatim text, the preferred term (PT), and the primary system organ class (SOC) will be listed.

Summaries of all TEAEs by treatment group for overall during the treatment-emergent period, during the 16-week treatment period, and during the follow-up period will include:

- The number (n) and percentage (%) of patient with at least 1 TEAE by SOC and PT
- TEAEs by severity (according to the grading scale outlined in Section 9.5.1), presented by SOC and PT
- TEAEs by relationship to treatment (related, not related), presented by SOC and PT

Deaths and other SAEs will be listed and summarized by treatment group.

Treatment-emergent adverse events leading to permanent treatment discontinuation will be listed and summarized by treatment group.

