3.2. The Safety Analysis Set (SAF)

The safety analysis set (SAF) includes all randomized patients who receive at least one injection of study drug and will be analyzed as treated. Treatment compliance/administration and all clinical safety variables will be summarized based on the SAF.

The “as treated” assignments will be made as follows:

Randomized to	Treatment Received	Treatment Assignment
Dupilumab (any regimen)	All placebo	Placebo
Dupilumab (any regimen)	≥ 1 Dupilumab (any regimen)	Original randomization group
Placebo	1 Dupilumab (any regimen)	Dupilumab regimen received
Placebo	> 1 Dupilumab (any regimen)	First Dupilumab regimen received [1]

[1] For example, a patient was randomized to Placebo group but received one 100mg Dupilumab and one 200mg Dupilumab accidentally. This patient will be assigned to 100mg Q2W Dupilumab treatment group.

In addition:

- Nonrandomized but treated patients will not be part of the safety population; however, their safety data will be presented separately.

- Randomized patients for whom it is unclear whether they took the study drug will be included in the safety population as randomized.

For safety summaries, three analysis periods are defined as follows:

- Week 16 treatment period is defined as
 - Day 1 to the study completion date of the planned Week 16 visit (or study day 113 starting from the first dose of study drug if the date of the Week 16 treatment visit is unavailable) for those patients who completed the 16 week treatment period
 - Day 1 to the date of early termination visit, for those patients who did not complete the 16 week treatment period
- Follow-up period is defined as the date after the week 16 visit date (or study day 113 starting from the first dose of study drug if the date of Week 16 treatment visit is unavailable) to the date of the end of study visit
- Overall study Period is defined as Day 1 to the date of the end of study visit

The SAF will be the basis for the analyses for the treatment period and overall study period; however, for the analyses for the follow-up period, only a subset of SAF will be included, which is defined as the patients who entered the follow-up period and had at least one visit after the week 16 treatment visit.

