5.8.1. Adverse Events

Listings of TEAEs, serious TEAEs, and TEAEs resulting in death and study drug discontinuation will be generated.

Number and proportions of patients reporting TEAEs will be summarized for overall during the study, during the week 16 treatment period and during the follow-up period separately, sorted by decreasing frequency of SOC and PT based on the overall incidence for the combined dupilumab treatment groups.

Summaries of TEAEs will include:

- TEAEs
 - TEAEs by SOC/PT
 - TEAEs by SOC/HLT/PT
 - TEAEs by PT
 - Common TEAEs by SOC/HLT/PT (incidence with PT $\geq 5\%$)
 - Common TEAEs by SOC/HLT/PT (incidence with PT $\geq 2\%$)
 - TEAEs by severity by SOC/PT

- Severe TEAEs by SOC/PT
- TEAEs related to study medication as assessed by the investigator by SOC/PT
- Severe TEAEs related to study medication as assessed by the investigator by SOC/PT
- Serious TEAEs by SOC/PT
 - Serious TEAEs by SOC/PT
 - Serious TEAEs by SOC/HLT/PT
 - Serious TEAEs related to study medication as assessed by the investigator by SOC/PT
- TEAEs leading to permanent discontinuation of study treatment by SOC/PT
- Death by SOC/PT
- AESI by AESI category (see [Appendix 10.4](#)) and SOC/PT

The time to first AESIs (TEAE category), serious TEAE, or TEAE leading to permanent treatment discontinuation during the treatment period will be assessed by Kaplan-Meier estimates (K-M plot). In order to detect any safety signals, the hazard ratio (HR) will be provided together with the corresponding 95% confidence interval (CI) for the selected adverse events during the treatment period only. Hazard ratios will be calculated using a Cox model including treatment group and randomization strata as factors. The time is defined as the date of first specific event – the date of first dose + 1. Patients without a specific event will be censored at the end of treatment period.

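### Overall-study safety percentages mix 16 weeks of observation for OLE entrants with 28 weeks for the others, and the follow-up set requires a later visit

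*Protocol*

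**What the plan says.** The Figure 2 note in Protocol 5.1 reads: "For patients who enter the OLE, week 16 is the end of study". Children who decline the OLE, or are not eligible for it, stay under observation: "For these patients, after week 16, follow-up visits will occur every 4 weeks from week 20 to week 28".

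SAP 3.2 sets the safety periods and denominators. "Overall study Period is defined as Day 1 to the date of the end of study visit", so its length depends on the child. On the denominator it says: "The SAF will be the basis for the analyses for the treatment period and overall study period". Follow-up tables use a subset of the SAF: "patients who entered the follow-up period and had at least one visit after the week 16 treatment visit".

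The summary measure is a count and a percentage. Protocol 10.5.3.1 lists "The number (n) and percentage (%) of patient with at least 1 TEAE by SOC and PT". SAP 5.8.1 says: "Number and proportions of patients reporting TEAEs will be summarized for overall during the study, during the week 16 treatment period", with follow-up as a third period. SAP 5.8.2 reports laboratory PCSVs as n (%) over the same three periods.

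Neither document plans a rate per unit of time at risk. The Kaplan-Meier and Cox safety analyses in SAP 5.8.1 cover the treatment period only. SAP 4.5.1 defines a follow-up TEAE by its onset after the week 16 visit, with no condition on later attendance.

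**The concern.** A crude percentage compares arms fairly only if children are observed for similar lengths of time in each arm. Here the length is fixed by an event after randomization. Entry to the OLE turns on family choice and on eligibility criteria that these documents do not give, so uptake could differ between arms. If it does, the arm with fewer entrants has more observed time and collects more events, even when the drug changes nothing. Neither document says which period is the one for comparing arms, and SAP 5.8.1 lists the overall period first.

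Laboratory PCSVs have a related problem. Children in follow-up have a scheduled week 28 hematology, chemistry and urinalysis sample (Table 2) that OLE entrants do not have in this study, and so one more chance to be flagged.

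The follow-up set is selected on something that happens during follow-up. Under SAP 4.5.1 a child can have a follow-up TEAE, and under SAP 3.2 the same child is outside the follow-up table because no visit came afterwards.

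**Working it through.** The plan states no figure on this point, so there is none to reproduce. The check is an illustration of size.

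**Inputs from the documents.** Week 16 is day 113 and week 28 is day 197 (Protocol Tables 1 and 2). The ratio is 197/113 = 1.74, or 28/16 = 1.75 in weeks. The planned size is about 110 per arm (Protocol 10.2).

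**Assumptions.** OLE uptake by arm is assumed, as is the event risk by week 16. The hazard is taken as constant to week 28 and equal in the arms, so any difference between arms is an artefact.

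**Formulas.** Let p16 be the risk by week 16 and a the OLE uptake.

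- Risk by week 28: p28 = 1 − (1 − p16)^(28/16).
- Crude overall percentage: a × p16 + (1 − a) × p28.
- Gap between arms: (a1 − a2) × (p28 − p16).

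**Mean observation, 95% versus 80% uptake.** 0.95 × 16 + 0.05 × 28 = 16.6 weeks, against 0.80 × 16 + 0.20 × 28 = 18.4 weeks.

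**Worked case, p16 = 30%.** p28 = 1 − 0.70^1.75 = 46.4%. At 95% uptake the overall percentage is 0.95 × 30 + 0.05 × 46.4 = 30.8%. At 80% it is 0.80 × 30 + 0.20 × 46.4 = 33.3%. The gap is 2.5 points.

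| p16 | p28 | Overall, 95% vs 80% uptake | Gap, 95% vs 80% | Gap, 95% vs 90% | Gap, 95% vs 70% |
|---|---|---|---|---|---|
| 5% | 8.6% | 5.2% vs 5.7% | 0.5 | 0.2 | 0.9 |
| 30% | 46.4% | 30.8% vs 33.3% | 2.5 | 0.8 | 4.1 |
| 60% | 79.9% | 61.0% vs 64.0% | 3.0 | 1.0 | 5.0 |

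Gaps are in percentage points. With a1 = a2 every gap is zero. A more extreme assumption, 90% versus 50% uptake with p16 = 50% (p28 = 70.3%), gives 0.40 × 20.3 = 8.1 points.

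**Size of the follow-up set.** At 95% uptake it is 110 × 0.05, about 6 children per arm. At 80% it is 110 × 0.20 = 22. These are counts before the later-visit condition removes anyone.

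**The case against.** The strongest reply is that the comparative safety analyses already use a common window. The skin-infection and serious-TEAE endpoints run through week 16 and are tested by CMH (SAP 5.7.2). The hazard ratios stop at the end of treatment. TEAEs and laboratory PCSVs are also tabulated for the 16-week period alone. Observation time (SAP 5.6) and the number entering the OLE (SAP 5.4) are both reported, so a reader can see that follow-up is unequal. All of this stands, and it confines the point to the overall-study and follow-up tables. A reader might infer that the trial's safety comparison as a whole is biased. The documents do not support that.

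The size rests on assumptions. No uptake is given, so neither a gap nor its direction can be predicted. The constant hazard is carried into time after the last dose, which is at week 14 or week 12. At 110 per arm the 2.5-point gap compares with a standard error of √[(0.308 × 0.692 + 0.333 × 0.667)/110], about 6.3 points. This also stands. The gap is systematic and not chance, but it is modest.

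On the follow-up set, a reader might infer that serious events after week 16 disappear from the report. They do not. The child stays in the SAF, in the overall table and in the listings, and SAEs are reported whether or not the child attends. SAP 3.2 asks for a visit, not a scheduled one, so an unscheduled or early termination visit can satisfy it. What remains is the child with no later visit of any kind.

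Patient-year rates have limits too. They pool on-drug and off-drug time, and they suit laboratory PCSVs poorly, because the only scheduled follow-up sample is at week 28. The fix allows for both. Dropping the visit condition brings in children with no observed follow-up, which can dilute the percentages, so their number should be shown.

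**Conclusion.** The point holds for two sets of tables. The crude overall-study TEAE and laboratory PCSV percentages are not comparable between arms if OLE uptake differs. Under equal constant hazards the artefact is about 0.5 to 3 points at an assumed 95% versus 80% uptake, about a third of that at 95% versus 90%, and zero at equal uptake. The follow-up table can omit a child whose event falls in the very period it describes. This is a narrow case, but the set may be small enough for one child to matter. No primary, secondary or model-based safety result changes. The change is worth making because it is cheap and prevents a difference in length of follow-up from being read as a drug effect in a pediatric safety table.

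**What to change.** 1. In SAP 5.8.1, name the 16-week treatment period as the comparative safety table for TEAEs and PCSVs. Label the overall-study tables descriptive, with unequal follow-up.
2. For the overall-period TEAE, serious TEAE and AESI summaries, add the number of patients with an event per 100 patient-years beside n (%), counting time to the first event or to the child's own end of study. State that this assumes a roughly constant hazard and mixes on-drug and off-drug time. Do not apply it to laboratory PCSVs.
3. In SAP 3.2, define the follow-up set as SAF patients who entered the follow-up period, meaning that they reached week 16 and did not enter the OLE. Remove the later-visit condition and report how many had no visit after week 16. State the date on which time at risk stops for those children, because the observation period in SAP 5.6 ends at the last visit.

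No new data are needed, since SAP 5.6 already derives observation time. The cost is some programming for time to first event in each tabulated row, and a slightly larger follow-up denominator.
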